Appendix 2 **Optional Shorter Infusion Substudy (cont.)**

Handling of Missing Data

For adverse events with a missing onset date, data will be imputed.

Missing assessments for continuous variables, such as physical examinations and vital signs, will not be imputed.

Determination of Sample Size

Based on the sample size of 100 patients used for analysis, the 95% CIs for some assumed Grade 3 or 4 IRRs are provided in Table 2.

Table 2: Determination of Substudy Sample Size

Number of Patients with Grade 3 or 4 IRRs	Grade 3 or 4 IRRs (%) (N=100)	95% CIs for Grade 3 or 4 IRRs (%)
1	1.00	(0.03, 5.45)
2	2.00	(0.24, 7.04)
3	3.00	(0.62, 8.52)
4	4.00	(1.10, 9.93)
5	5.00	(1.64, 11.28)
6	6.00	(2.23, 12.60)
7	7.00	(2.86, 13.89)

The 95% CIs for the IRR (%) are calculated based on the Clopper and Pearson method.

Appendix 2

Optional Shorter Infusion Substudy (cont.)

Table 3: Substudy Schedule of Activities

	Week 96 Treatment Visit (± 14 days)	Substudy Follow-up Visit (30 ± 14 days later) ^a
Informed consent^b	x	
Review inclusion and exclusion criteria	x	
Physical examination^c	x	x
Weight	x	
Vital signs^d	x	x
Brain MRI^e	x	
Pregnancy test^f	x	
Adverse event assessment^g	x	x
Concomitant treatment review	x	x^h
Methylprednisolone and antihistamine premedicationⁱ	x	
Ocrelizumab administration	x	

eCRF=electronic case report form; IRR=infusion-related reaction; IV=intravenous; MRI=magnetic resonance imaging; PML=progressive multifocal leukoencephalopathy.

^a Conducted 30 days after the shorter infusion with ocrelizumab.

^b Written informed consent will be obtained from all patients in order to be eligible for the study and prior to any study procedures.

^c A limited physical examination may be conducted. Any abnormality identified should be recorded on the eCRF. New or worsened clinically significant abnormalities should be recorded as adverse events, if appropriate.

^d Vital signs will include the measurements of heart rate, systolic and diastolic blood pressures, and temperature. Vital signs should be taken approximately 45 minutes prior to the premedication methylprednisolone infusion. In addition, vital signs should be obtained prior to the ocrelizumab infusion then approximately every 15 minutes for the first hour, followed by approximately every 30 minutes until 1 hour after the end of the infusion.

^e Should only be done if PML is suspected, and should not be done in addition to an MRI at Week 96 conducted in the main study. If needed, should be done pre-dose.

^f Pregnancy test should not be done in addition to the pregnancy test at Week 96 conducted in the main study. If needed, should be done pre-dose.

^g After informed consent has been obtained but prior to initiation of study drug, only serious adverse events caused by a protocol-mandated intervention (e.g., invasive procedures such as biopsies, discontinuation of medications) should be reported. After initiation of study drug, related serious adverse events must be collected and reported regardless of the time elapsed from the study drug administration, even if the substudy has been closed. Unrelated serious adverse events must be collected and reported during the substudy and substudy follow-up. Non-serious adverse events have to be reported until the end of substudy follow-up.

^h Medications used after treatment discontinuation should be recorded during substudy follow-up.

ⁱ All patients must receive prophylactic treatment with 100 mg methylprednisolone (or equivalent), to be completed approximately 30 minutes before the start of each ocrelizumab infusion, and with an antihistaminic drug (e.g., diphenhydramine) approximately 30–60 minutes before each infusion of ocrelizumab. Prophylactic treatment with an analgesic/antipyretic (e.g., 1 g acetaminophen) is strongly recommended 30–60 minutes prior to the start of ocrelizumab infusion to reduce the risk of IRRs.

Ocrelizumab—Genentech, Inc.

86/ Protocol MN30035, Version 5

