5.3.1 Adverse Event Reporting Period

Investigators will seek information on adverse events at each patient contact. All adverse events, whether reported by the patient or noted by study personnel, will be recorded in the patient's medical record and on the Adverse Event eCRF.

After informed consent has been obtained **but prior to initiation of study drug**, only serious adverse events caused by a protocol-mandated intervention (e.g., invasive procedures such as biopsies, discontinuation of medications) should be reported (see Section 5.4.2 for instructions for reporting serious adverse events).

After initiation of study drug, related serious adverse events must be collected and reported regardless of the time elapsed from the last study drug administration, even if the study has been closed (see Section 5.4.2).

Unrelated serious adverse events must be collected and reported during the study through the end of the Safety Follow-Up Period, which is at least 24 weeks after the last infusion but may be extended in patients whose B cells take longer to replete.

Non-serious adverse events have to be reported until the end of the Safety Follow-up Period.

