5.3.5.8 Deaths

All deaths that occur during the protocol-specified, adverse event, reporting period (see Section 5.3.1), regardless of relationship to study drug, must be recorded on the Adverse Event eCRF and immediately reported to the Sponsor (see Section 5.4.2). This includes death attributed to progression of RRMS.

Death should be considered an outcome and not a distinct event. The event or condition that caused or contributed to the fatal outcome should be recorded as the single medical concept on the Adverse Event eCRF. Generally, only one such event should be reported. The term "**sudden death**" should be used only for the occurrence of an abrupt and unexpected death due to presumed cardiac causes in a patient with or without preexisting heart disease, within 1 hour after the onset of acute symptoms or, in the case of an unwitnessed death, within 24 hours after the patient was last seen alive and stable. If the cause of death is unknown and cannot be ascertained at the time of reporting, "**unexplained death**" should be recorded on the Adverse Event eCRF. If the cause of death later becomes available (e.g., after autopsy), "unexplained death" should be replaced by the established cause of death.

If the death is attributed to progression of RRMS, "RRMS progression" should be recorded on the Adverse Event eCRF.

Ocrelizumab—Genentech, Inc.
53/ Protocol MN30035, Version 5

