5.4.2.2 Events That Occur after Study Drug Initiation

After initiation of study drug, serious adverse events and adverse events of special interest will be reported for at least 24 weeks after the last dose of study drug.

Investigators should record all case details that can be gathered immediately (i.e., within 24 hours after learning of the event) on the Adverse Event eCRF and submit the report via the electronic data capture (EDC) system. A report will be generated and sent to Safety Risk Management by the EDC system.

In the event that the EDC system is unavailable, the Serious Adverse Event/Adverse Event of Special Interest Reporting Form provided to investigators should be completed and submitted to the Sponsor or its designee immediately (i.e., no more than 24 hours after learning of the event), either by faxing or by scanning and emailing the form using the fax number or email address provided to investigators. Once the EDC system is available, all information will need to be entered and submitted via the EDC system.

Instructions for reporting post-study adverse events are provided in Section [5.6](#).

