5.6 POST-STUDY ADVERSE EVENTS

The Sponsor should be notified if the investigator becomes aware of any serious adverse event that occurs after the end of the adverse event reporting period (defined as at least 24 weeks after the last dose of study drug), if the event is believed to be related to prior study drug treatment.

These events should be reported through use of the Adverse Event eCRF. However, if the EDC system is not available, the investigator should report these events directly to the Sponsor or its designee, either by faxing or by scanning and emailing the paper Clinical Trial Serious Adverse Event/Adverse Event of Special Interest Reporting Form using the fax number or email address provided to investigators.

5.7 EXPEDITED REPORTING TO HEALTH AUTHORITIES, INVESTIGATORS, INSTITUTIONAL REVIEW BOARDS, AND ETHICS COMMITTEES

The Sponsor will promptly evaluate all serious adverse events and adverse events of special interest against cumulative product experience to identify and expeditiously communicate possible new safety findings to investigators, IRBs, and applicable health authorities based on applicable legislation.

To determine reporting requirements for single adverse event cases, the Sponsor will assess the expectedness of these events using the following reference document:

- Ocrelizumab Investigator's Brochure

The Sponsor will compare the severity of each event and the cumulative event frequency reported for the study with the severity and frequency reported in the applicable reference document.

Reporting requirements will also be based on the investigator's assessment of causality and seriousness, with allowance for upgrading by the Sponsor as needed.

Refer to the Ocrelizumab Investigator's Brochure for a list of serious adverse drug reactions.

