- ^t After informed consent has been obtained but prior to initiation of study drug, only serious adverse events caused by a protocol-mandated intervention (e.g., invasive procedures such as biopsies, discontinuation of medications) should be reported. After initiation of study drug, related serious adverse events must be collected and reported regardless of the time elapsed from the last study drug administration, even if the study has been closed. Unrelated serious adverse events must be collected and reported during the study through the end of the Safety Follow-up period, which is at least 24 weeks after the last infusion but may be extended in patients whose B cells take longer to replete. Non-serious adverse events have to be reported until the end of the Safety Follow-up Period.
- ^u Medications used after treatment discontinuation should be recorded during the Safety Follow-up Period.
- ^v All patients must receive prophylactic treatment with 100 mg methylprednisolone (or equivalent), to be completed approximately 30 minutes before the start of each ocrelizumab infusion, and with an antihistaminic drug (e.g., diphenhydramine) approximately 30–60 minutes before each infusion of ocrelizumab. Prophylactic treatment with an analgesic/antipyretic (e.g., 1 g acetaminophen) is strongly recommended 30–60 minutes prior to the start of ocrelizumab infusion to reduce the risk of IRRs.
- ^w Dose 1 of ocrelizumab will be administered as two 300-mg IV infusions (600 mg total) separated by 14 days (i.e., Days 1 and 15). Subsequent doses will be administered as one 600-mg IV infusion every 24 weeks for a maximum of 4 doses.

Ocrelizumab—Genentech, Inc.
78/ Protocol MN30035, Version 5

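### The substudy adverse-event footnote sets a reporting window of about 30 days for unrelated serious and non-serious events, inconsistent with the 24-week minimum elsewhere in the protocol

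*Protocol*

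**What the plan says.** **Substudy rule.** Footnote g is attached to the adverse-event row of the substudy schedule (Protocol Appendix 2, Table 3). It keeps related serious events reportable without a time limit. For the rest it says "Unrelated serious adverse events must be collected and reported during the substudy and substudy follow-up" and "Non-serious adverse events have to be reported until the end of substudy follow-up". The SAP carries the same footnote (Appendix 6, Appendix A, footnote g). Table 3 and the Substudy Follow-up text make that follow-up a single clinic visit at 30 days, with a window of ± 14 days. The Appendix 2 Safety Plan gives 30 days as a minimum for recording events. After 30 days, patients who do not move to commercial ocrelizumab are permitted, but not required, to continue in main-study safety follow-up.

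**Main-body rules.**
- Section 5.4.2.2: "serious adverse events and adverse events of special interest will be reported for at least 24 weeks after the last dose of study drug".
- Section 5.6 defines the adverse-event reporting period with the same 24-week minimum, also counted from the last dose.
- Section 5.3.1 has unrelated serious events reported "through the end of the Safety Follow-Up Period, which is at least 24 weeks after the last infusion", and non-serious events until that period ends.
- Section 5.1 has all adverse and serious adverse events recorded for at least 24 weeks after the treatment period ends. Section 3.6 puts that end at about Week 100 for substudy patients.
- Section 5.3.5.8 covers "All deaths that occur during the protocol-specified, adverse event, reporting period", whatever their relationship to study drug.

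**Parallel footnote.** Footnote t of the main-study schedule (Appendix 1) is worded almost identically to footnote g, but has unrelated serious events reported "through the end of the Safety Follow-up period, which is at least 24 weeks after the last infusion". Footnote g has the substudy follow-up in that place.

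**The concern.** Substudy patients receive an extra infusion at Week 96, so for them the clock in Sections 5.4.2.2 and 5.6 restarts at Week 96 and runs to Week 120. Neither section exempts the substudy, and Appendix 2 nowhere says that it overrides Section 5. Yet the footnote a coordinator would consult for the adverse-event row points to a period ending about four weeks after the infusion. The protocol does not say which rule governs.

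What is at stake is capture of serious events judged unrelated. Relatedness is the investigator's yes/no call (Section 5.3.4). The sponsor can upgrade that call (Section 5.7), but only for events it receives. Deaths depend on the same reporting period. Patients also remain pharmacologically exposed well past day 30: Section 5.1.3.1.4 gives a median time to B-cell repletion of 72 weeks.

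**Working it through.** No planned figure is in dispute. The check sets the texts side by side, adds date arithmetic, and then bounds the number of events.

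**1. Which rules apply to a substudy patient**
- *Serious events, related or not:* Sections 5.4.2.2 and 5.6 count from the last dose, which is Week 96. Minimum end: 96 + 24 = Week 120.
- *All events:* Section 5.1 counts from the end of the treatment period, which Section 3.6 places at about Week 100. Minimum end: 100 + 24 = about Week 124.
- *Non-serious events under Section 5.3.1:* these are tied to the Safety Follow-up Period. Section 3.1 limits that period to patients who discontinue or do not go on to commercial drug, and Appendix 1 footnote b starts it at the Week 72 infusion with assessment at Week 96. Section 5.3.1 is therefore the weaker basis for the non-serious conflict; Sections 5.1 and 3.6 carry it better.
- *Footnote g:* unrelated serious and non-serious events are tied to the visit at day 30 (30 − 14 = day 16 to 30 + 14 = day 44). That is Week 96 + 30/7 = 100.3 (98.3 to 102.3).

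**2. Length of the gap against the 24-week minimum after the last dose**
- 24 weeks × 7 = 168 days.
- Visit at day 30: 168 − 30 = 138 days, or 19.7 weeks; 138/168 = 82%.
- Visit at day 44: 168 − 44 = 124 days, or 17.7 weeks; 124/168 = 74%.
- Visit at day 16: 168 − 16 = 152 days, or 21.7 weeks; 152/168 = 90%.

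**3. Upper bound on serious events in the gap**
- Input: 6.9% of ocrelizumab patients in the pooled relapsing-MS trials had a serious event over 96 weeks (Protocol Section 1.2.1.2); 96 × 7 = 672 days.
- Assumption: that risk applies here at a constant rate.
- Formula for 100 patients: 100 × [1 − (1 − 0.069)^(gap/672)].
- Gap of 138 days: 1.46. Gap of 124 days: 1.31. Gap of 152 days: 1.60.

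Given that rate, this bounds the loss from above. It counts related as well as unrelated events, and it assumes that none of the 100 patients continues in main-study follow-up. The source rate also covers periods with infusions, while the gap contains no study infusion.

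**4. Substudy outcome**

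Section 5.3.5.1 defines infusion-related reactions as occurring during or within 24 hours of administration. Even the earliest visit, day 16, falls after that, so the Grade 3 or 4 outcome does not depend on the gap.

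**The case against.** The strongest reply is that nothing is lost. Section 5.4.2.2 is unconditional, Appendix 2 does not displace it, and footnote g, for serious events, says only what must be collected during the substudy. A reader might infer that footnote g orders sites to stop collecting unrelated serious events at the follow-up visit. The text does not support that: the serious-event sentence contains no limiting word and no stop instruction. On the reading that Section 5.4.2.2 still binds, only a cross-reference is missing. This stands, and it makes the loss conditional on a site using the footnote alone.

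A second reply is that 30 days looks deliberate. Appendix 2 has its own safety plan, follow-up and schedule, all set at about 30 days or Week 100, for one extra dose of an approved drug. That is plausible, particularly for non-serious events. A reader might call the non-serious sentence an unavoidable contradiction of Section 5.3.1. It is not, because of how the Safety Follow-up Period is bounded in Section 3.1 and Appendix 1 footnote b. The conflict remains against Section 5.1 read with Section 3.6, and no text declares an exception.

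Third, few serious events should fall into the unrelated class. Table 4 in Section 5.3.4 makes relatedness the default, related serious events have no time limit, and events of special interest stay under Section 5.4.2.2. This stands. The documents do not allow the unrelated share to be estimated, so only the bound for all serious events can be given.

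**Conclusion.** The footnote needs correcting as written, because the protocol gives sites two different windows for the same events. For serious events the inconsistency is with Sections 5.4.2.2 and 5.6; for all events it is with Section 5.1 read with Section 3.6.

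The possible shortfall is 138 of 168 days (124 to 152) for a patient whose site follows footnote g alone, and zero for serious events if the site follows Section 5.4.2.2. Under the constant-rate assumption, at most about 1.5 of 100 patients (1.3 to 1.6) would have any serious event in that interval, and fewer an unrelated one. Unrelated deaths are exposed only on the same less favourable reading.

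The practical effect is small, and no substudy objective is harmed. The reason to act is that the protocol already states the correct rule for serious events and the footnote obscures it. A reader might go further and conclude that main-study follow-up should become the expected course after day 30. The inconsistency does not require that: it would in effect add a visit and could prolong the study, which is a trade-off and not a correction.

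**What to change.** 1. Amend footnote g in Protocol Appendix 2, Table 3, and its copy in SAP Appendix 6, Appendix A. State that all serious adverse events, related or not, are reported for at least 24 weeks after the Week 96 infusion, in line with Section 5.4.2.2. Collection can be by contact, without an added visit.
2. If the window of roughly 30 days for non-serious events is intended, state it as a substudy exception in Sections 5.1 and 5.3.1.
3. Leave the permissive wording on continued main-study follow-up in Appendix 2 unchanged.

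The cost is a wording change in two documents and modest extra serious-event reporting by sites for about 20 weeks, to about Week 120, including for patients on commercial drug. The substudy tables need no change, because SAP Appendix 6 already limits that analysis to Week 96 and the substudy follow-up.

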Appendix 3 Expanded Disability Status Scale (EDSS)

Kurtzke Expanded Disability Status Scale (EDSS)

- 0.0 - Normal neurological exam (all grade 0 in all Functional System (FS) scores*).
- 1.0 - No disability, minimal signs in one FS* (i.e., grade 1).
- 1.5 - No disability, minimal signs in more than one FS* (more than 1 FS grade 1).
- 2.0 - Minimal disability in one FS (one FS grade 2, others 0 or 1).
- 2.5 - Minimal disability in two FS (two FS grade 2, others 0 or 1).
- 3.0 - Moderate disability in one FS (one FS grade 3, others 0 or 1) or mild disability in three or four FS (three or four FS grade 2, others 0 or 1) though fully ambulatory.
- 3.5 - Fully ambulatory but with moderate disability in one FS (one grade 3) and one or two FS grade 2; or two FS grade 3 (others 0 or 1) or five grade 2 (others 0 or 1).
- 4.0 - Fully ambulatory without aid, self-sufficient, up and about some 12 hours a day despite relatively severe disability consisting of one FS grade 4 (others 0 or 1), or combination of lesser grades exceeding limits of previous steps; able to walk without aid or rest some 500 meters.
- 4.5 - Fully ambulatory without aid, up and about much of the day, able to work a full day, may otherwise have some limitation of full activity or require minimal assistance; characterized by relatively severe disability usually consisting of one FS grade 4 (others or 1) or combinations of lesser grades exceeding limits of previous steps; able to walk without aid or rest some 300 meters.
- 5.0 - Ambulatory without aid or rest for about 200 meters; disability severe enough to impair full daily activities (e.g., to work a full day without special provisions); (Usual FS equivalents are one grade 5 alone, others 0 or 1; or combinations of lesser grades usually exceeding specifications for step 4.0).
- 5.5 - Ambulatory without aid for about 100 meters; disability severe enough to preclude full daily activities; (Usual FS equivalents are one grade 5 alone, others 0 or 1; or combination of lesser grades usually exceeding those for step 4.0).
- 6.0 - Intermittent or unilateral constant assistance (cane, crutch, brace) required to walk about 100 meters with or without resting; (Usual FS equivalents are combinations with more than two FS grade 3+).

Appendix 3

Expanded Disability Status Scale (EDSS) (cont.)

- 6.5 - Constant bilateral assistance (canes, crutches, braces) required to walk about 20 meters without resting; (Usual FS equivalents are combinations with more than two FS grade 3+).
- 7.0 - Unable to walk beyond approximately 5 meters even with aid, essentially restricted to wheelchair; wheels self in standard wheelchair and transfers alone; up and about in wheelchair some 12 hours a day; (Usual FS equivalents are combinations with more than one FS grade 4+; very rarely pyramidal grade 5 alone).
- 7.5 - Unable to take more than a few steps; restricted to wheelchair; may need aid in transfer; wheels self but cannot carry on in standard wheelchair a full day; May require motorized wheelchair; (Usual FS equivalents are combinations with more than one FS grade 4+).
- 8.0 - Essentially restricted to bed or chair or perambulated in wheelchair, but may be out of bed itself much of the day; retains many self-care functions; generally has effective use of arms; (Usual FS equivalents are combinations, generally grade 4+ in several systems).
- 8.5 - Essentially restricted to bed much of day; has some effective use of arm(s); retains some self-care functions; (Usual FS equivalents are combinations, generally 4+ in several systems).
- 9.0 - Helpless bed patient; can communicate and eat; (Usual FS equivalents are combinations, mostly grade 4+).
- 9.5 - Totally helpless bed patient; unable to communicate effectively or eat/swallow; (Usual FS equivalents are combinations, almost all grade 4+).
- 10.0 - Death due to MS.

*Excludes cerebral function grade 1.

Note 1: EDSS steps 1.0 to 4.5 refer to patients who are fully ambulatory and the precise step number is defined by the Functional System score(s). EDSS steps 5.0 to 9.5 are defined by the impairment to ambulation and usual equivalents in Functional Systems scores are provided.

Note 2: EDSS should not change by 1.0 step unless there is a change in the same direction of at least one step in at least one FS.

Sources: Kurtzke JF. Rating neurologic impairment in multiple sclerosis: an expanded disability status scale (EDSS). *Neurology*. 1983 Nov;33(11):1444-52.

Source: [http://www.nationalmssociety.org/For-Professionals/Researchers/Resources-for-Researchers/Clinical-Study-Measures/Functional-Systems-Scores-\(FSS\)-and-Expanded-Disab](http://www.nationalmssociety.org/For-Professionals/Researchers/Resources-for-Researchers/Clinical-Study-Measures/Functional-Systems-Scores-(FSS)-and-Expanded-Disab)

Ocrelizumab—Genentech, Inc.
88/ Protocol MN30035, Version 5

Appendix 4
2010 Revised McDonald Diagnostic Criteria for Multiple Sclerosis

Clinical (attacks)	Lesions	Additional Criteria to Make Diagnosis
2 or more	Objective clinical evidence of 2 or more lesions or objective clinical evidence of 1 lesion with reasonable historical evidence of a prior attack	None. Clinical evidence alone will suffice; additional evidence desirable but must be consistent with MS
2 or more	Objective clinical evidence of 1 lesion	Dissemination in space, demonstrated by 
 • ≥ 1 T2 lesion in at least two MS typical CNS regions (periventricular, juxtacortical, infratentorial, spinal cord); OR 
 • Await further clinical attack implicating a different CNS site
1	Objective clinical evidence of 2 or more lesions	Dissemination in time, demonstrated by 
 • Simultaneous asymptomatic contrast-enhancing and non-enhancing lesions at any time; OR 
 • A new T2 and/or contrast-enhancing lesions(s) on follow-up MRI, irrespective of its timing; OR 
 • Await a second clinical attack
1	Objective clinical evidence of 1 lesion	Dissemination in space, demonstrated by 
 • ≥ 1 T2 lesion in at least two MS typical CNS regions (periventricular, juxtacortical, infratentorial, spinal cord); OR 
 • Await further clinical attack implicating a different CNS site AND Dissemination in time, demonstrated by 
 • Simultaneous asymptomatic contrast-enhancing and non-enhancing lesions at any time; OR 
 • A new T2 and/or contrast-enhancing lesions(s) on follow-up MRI, irrespective of its timing; OR 
 • Await a second clinical attack

Ocrelizumab—Genentech, Inc.
89/ Protocol MN30035, Version 5

Appendix 4
2010 Revised McDonald Diagnostic Criteria for Multiple Sclerosis (cont.)

Clinical (attacks)	Lesions	Additional Criteria to Make Diagnosis
0 (progression from onset)		
One year of disease progression (retrospective or prospective) AND at least 2 out of 3 criteria:
 
 • Dissemination in space in the brain based on ≥ 1 T2 lesion in periventricular, juxtacortical or infratentorial regions; • Dissemination in space in the spinal cord based on ≥ 2 T2 lesions; 
OR
 
 • Positive CSF
2 or more	Objective clinical evidence of 2 or more lesions or objective clinical evidence of 1 lesion with reasonable historical evidence of a prior attack	
None. Clinical evidence alone will suffice; additional evidence desirable but must be consistent with MS

CNS=central nervous system; CSF=cerebrospinal fluid; MRI=magnetic resonance imaging; MS=multiple sclerosis.

Sources:

http://www.nationalmssociety.org/NationalMSSociety/media/MSNationalFiles/Brochures/Paper-TipSheet_-2010-Revisions-to-the-McDonald-Criteria-for-the-Diagnosis-of-MS.pdf

Polman et al. 2011.

Ocrelizumab—Genentech, Inc.
90/ Protocol MN30035, Version 5

Appendix 5

New York Heart Association Classification of Functional Cardiac Capacity

Class	Description
I	No limitation: Ordinary physical activity does not cause undue fatigue, dyspnea, or palpitation.
II	Slight limitation of physical activity: Such patients are comfortable at rest. Ordinary physical activity results in fatigue, palpitations, dyspnea, or angina.
III	Marked limitation of physical activity: Although patients are comfortable at rest, less than ordinary physical activity will lead to symptoms.
IV	Inability to carry on physical activity without discomfort: Symptoms of congestive heart failure are present even at rest. With any physical activity, increased discomfort is experienced.

From: Criteria Committee, New York Heart Association, Inc. Diseases of the heart and blood vessels. Nomenclature and criteria for diagnosis. 6th ed. Boston, Little, Brown and Co, 1964:114.

Ocrelizumab—Genentech, Inc.
91/ Protocol MN30035, Version 5

